Random assignment will be followed by 8 weeks of treatment with NAC or placebo. Study medications will be identical in appearance. Participants will be provided with 10 days of medication at each weekly visit to increase the likelihood of medication continuity in case of a missed visit. Extra medication will be collected from participants at each visit. Study medication (NAC or placebo) will be started at a dose of 600 mg bid (1200 mg per day), for 3 days, then 1200 mg bid for 4 days, (2400 mg per day), then 1800 mg bid (3600 mg per day) for weeks 2 through 8. Similar doses have been shown to be an effective dose in other addiction studies (see A.2.). If the participant experiences significant side effects during the titration period, the dosage may be adjusted as necessary. Patients will be treated with the highest dose tolerated, not to exceed a total of 3600 mg per day, but may be reduced by 600mg increments as needed. Wellspring Compounding Pharmacy, a compounding Pharmacy – a compounding pharmacy recommended by the University of California, San Francisco School of Medicine Pharmacy -- will supply NAC study capsules and matching placebo capsules. The policies and procedures concerning good compounding practices and environmental, instrumental and procedural quality assurance have been approved by the California State Board of Pharmacy. The SFVAMC Research Pharmacist will directly receive all study medications from Wellspring Compounding Pharmacy and store in appropriate environmental conditions. The dosage is to be determined by a study physician at each weekly visit, using the titration schedule as a guide. An official VA prescription form must be filled out by a study physician for each patient at each visit. A research associate will pick up the prescription from the SFVAMC pharmacy. The date, time and amount of study compound dispensed will also be recorded in the subject's electronic medical file. Participants are instructed to return all unused study medication weekly. The number of returned capsules will be documented.

D.3.h. Medical Management

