Efforts will be made toward reducing the amount of missing data by: (a) use of a collateral informant to assist in locating patients; (b) telephone follow-up to make contact with missing patients; (c) establishment of flexible, but acceptable, time periods for the completion of each assessment; and (d) some self-report and interview measures may be administered by telephone to collect missing data from patients unwilling or unable to visit research sites to participate in a scheduled assessment session. All phone visits will include a Medical Management counseling session, during which a trained psychologist or psychiatrist (the Medical Manager) will assess adverse effects, concomitant medications, suicidality and general well-being. During phone visits, study coordinators will skip the question on the Adverse Event checklist, "Have you had suicidal thoughts or actions since the last study visit". Instead, the Medical Manager will ask that question and report back to coordinator after the Medical Management counseling session. If a Medical Management counseling session becomes logistically impossible, the PI will file a protocol violation.

Establishment of flexible, but acceptable time frames for completion of research assessments: All research assessments should be completed within an established window. Assessments scheduled for weeks 1, 2,3,5, 6, and 7 will have a window of ± 3 days for completion. Assessments scheduled for weeks 4, 8, and 12, have a window of ± 1 week for completion. This flexibility will enhance the ability of staff to schedule patients for assessments as close as possible to the protocol defined period. Patients likely to miss appointments should be scheduled early in the window to allow for successive attempts to complete ratings within the desired time frame.

After receiving CHR and R&D approval, we will be converting most of our questionnaire measures to a digital format, so that this questionnaire data can be collected and managed using the San Francisco VA Medical Center's Stress and Health Research Program Data Management Research Database System.

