Alcohol and drug use will be assessed using the Time-Line Follow-Back (TLFB)_1^{135,136}. This is a self-report test which will be performed at baseline/screening and will cover the 12 weeks prior to entry, with particular attention to the 4 weeks immediately preceding entry to the study. In addition, the TLFB will be done weekly for the preceding 7 days at weeks 1-8, and at week 12. The TLFB will be used to calculate percent of days abstinent from alcohol, drinks per drinking day, and percent heavy drinking days. The (TLFB) is a method to assess the quantity of alcohol consumption on a daily basis. With a calendar as a guide, the participant provides a retrospective estimate of daily drinking over a specified period. For this study participants will estimate their daily drinking for the 28-day period prior to the initial screening and for the 7-day period prior to each weekly visit. The TLFB provides a calendar of the targeted period for recording the number of standard drinks consumed on each day. The TLFB can be used to obtain the number of days on which drinking occurred and the number of drinks per day. Standard Drink Conversions will be used to standardize all participant reports of alcohol consumption ⁸.

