The following variables will be derived from the standard drinks consumed per day: 1) Percent Days Abstinent (the number of non-drinking days divided by the number of study days) 2) Percent Heavy Drinking Days (the number of days for which the number of drinks was at least 5 drinks for men and at least 4 drinks for women, divided by the number of study days); 3) Drinks/Day (the number of drinks consumed divided by the number of study days); and 4) Drinks/Drinking Day. The TLFB will be administered in interview format. It takes 5-10 minutes to complete the TLFB for a 28-day period. Interviewers require no clinical expertise but some training. Prior to reviewing alcohol use, the interviewer will prepare the TLFB calendar outlining the time period to be assessed and noting holidays and other general important or newsworthy events that have occurred (e.g., Super Bowl Sunday). During Screening and at each weekly visit thereafter, participants will be provided with a diary card for recording the number of drinks consumed each day. The diary is intended as a memory aid and interviewers should discuss and verify any information collected on the diary and verify if any days without entries are actually non-drinking days or drinking occurrences that were not recorded. Differences will be discussed with the participant and the site personnel will clarify the number of drinks per day.

Cigarette (Brown et al. 1998) and other non-alcohol substance use will also be collected using the Timeline Followback. Participants are shown the same calendars used for Alcohol TLFB and asked to use recall to record the number of cigarettes smoked and days of cannabis, cocaine, opiate, and methamphetamine use. Cigarette and other non-alcohol substance use TLFB data will be collected at baseline for the previous 28 day time period. Data will also be collected at each subsequent visit for the time since the last visit. Purpose: To calculate the primary outcome measure, PHDD. To assess alcohol use frequency and amount on a daily basis, in order to calculate percent of days abstinent from alcohol, drinks per drinking day, and percent heavy drinking days and to assess cigarette and other non-alcohol substance use frequency.

Time required for administration: The initial assessment requires 10-15 minutes; subsequent weekly administration takes 5 minutes. Frequency of administration: Baseline and weekly during weeks 1-8 and week 12.

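### Alcohol TLFB looks back only 7 days at each visit, so primary-outcome days before a late visit or after a missed one need not be collected (minor)

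*Combined protocol and SAP*

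**What the plan says.** Section D.4.d.1 derives PHDD, the primary drinking outcome, from the alcohol TLFB and states the look-back after baseline twice. First, "the TLFB will be done weekly for the preceding 7 days at weeks 1-8, and at week 12". Then participants are to estimate their daily drinking "for the 7-day period prior to each weekly visit". The summary of measures in D.3.i lists the TLFB weeks but gives no look-back after baseline.

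A later paragraph of D.4.d.1, on cigarettes and other non-alcohol substances, has a different rule: "Data will also be collected at each subsequent visit for the time since the last visit". The same section defines PHDD as heavy drinking days over the number of study days. It also says that "participants will be provided with a diary card for recording the number of drinks consumed each day", calls the diary a memory aid, and tells interviewers to check days left blank.

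On timing, D.4.a says that visits at weeks 1, 2, 3, 5, 6 and 7 "will have a window of ± 3 days for completion", and "Assessments scheduled for weeks 4, 8, and 12, have a window of ± 1 week for completion". In D.3.g participants are "provided with 10 days of medication at each weekly visit to increase the likelihood of medication continuity in case of a missed visit". D.4.a also allows some self-report and interview measures to be taken by telephone, without naming the TLFB.

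**The concern.** A fixed 7-day look-back covers every day only if visits are never more than 7 days apart. The plan's own windows and its provision for missed visits allow longer gaps. When one occurs, the alcohol rule as written does not ask about the earliest days, although the participant is present and may hold a diary card for them. The rule for cigarettes would capture them.

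The denominator makes this more than a matter of wording. Dividing by study days presumes that drinking on each day is known. If an uncollected day stays in the denominator, it counts as a day without heavy drinking, and the plan does not say how such days are handled.

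At stake is the completeness and precision of PHDD in a 30-person pilot that D.3.i expects to supply variability estimates for a larger trial.

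**Working it through.** The plan gives no figure of its own on this point, so there is none to reproduce.

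**1. Days not covered.** With gap G between consecutive completed TLFBs, uncovered days = G − 7 when G exceeds 7. Windows are from D.4.a and the drug supply is from D.3.g.

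| Situation | G (days) | Uncovered |
|---|---|---|
| All visits on schedule | 7 | 0 |
| Gap equal to the drug supply, or a ±3-day visit at its latest after an on-time visit (7 + 3) | 10 | 3 |
| One visit missed, neighbours on time (2 × 7) | 14 | 7 |
| Week 1 earliest, week 2 latest (7 + 3 + 3) | 13 | 6 |
| Week 3 earliest, week 4 latest (7 + 3 + 7) | 17 | 10 |

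The last two rows are limits on paper. They are unlikely, because both gaps exceed the 10-day supply.

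**2. Denominator.** Over 8 weeks there are 56 study days. If 7 are uncollected but stay in the denominator, PHDD falls by 7/56 = 12.5% of its value when the lost days resemble the rest; for example, 50% becomes 50 × 49/56 = 43.75%. This shows what the written definition permits, not what the plan says will be done.

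**3. Recoverable person-weeks.** Table 5 in D.3.i reports, for the earlier topiramate trial, 80.88% of visits attended and 81.25% of participants attending week 12. Applying these here is an assumption. Weekly TLFBs planned: 30 × 8 = 240. Missed: (1 − 0.8088) × 240 = 45.9. Only weeks followed by a later contact can be recovered.

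- Lower end: the 18.75% who do not reach week 12 all leave before week 1. Recoverable = (0.1912 − 0.1875) × 240 = 0.9, about 1.
- Upper end: nobody drops out and each visit is missed independently with p = 0.1912. Per person, 8p − p(1 − p⁸)/(1 − p) = 1.530 − 0.236 = 1.293 missed weeks are followed by an attended visit in weeks 1-8. Times 30 gives 38.8, about 39. Catch-up at week 12 could add at most the remaining 45.9 − 38.8 = 7.1.

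**4. Effect on the estimates (assumed illustration).** Simulation of 20,000 trials: 15 per arm, 8 weeks, PHDD 50% v 30%, person SD 1.5 and week SD 0.7 on the logit scale. Of the participants, 18.75% leave at a uniformly random week. In-study visits are missed with probability 9.56% (half of 19.12%), or with probability rising linearly with that week's heavy days. Catch-up includes the week-12 visit. Each pair is the 7-day rule v catch-up.

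| Chance of a missed visit | SE of slope difference | Ratio | SE of arm difference | Arm difference |
|---|---|---|---|---|
| 9.56% throughout | 1.249 v 1.176 | 1.06 | 9.51 v 9.47 | 20.02 v 20.03 |
| 6% to 13% | 1.238 v 1.176 | 1.05 | 9.43 v 9.39 | 19.93 v 19.99 |
| 3% to 16% | 1.237 v 1.180 | 1.05 | 9.45 v 9.44 | 19.92 v 19.99 |
| 0% to 22% | 1.235 v 1.180 | 1.05 | 9.40 v 9.40 | 19.72 v 19.88 |

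In the first row, weeks with data are 81.0% v 89.3%, or 0.083 × 240 = 20 person-weeks, inside the range in step 3. Without week-12 catch-up the 89% becomes about 88%. With complete data the slope SE is about 1.08.

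**The case against.** The best defence is that D.4.d.1 describes an on-schedule week, when the preceding 7 days and the time since the last visit are the same period. The other substances use the same calendar, and the since-last-visit sentence is followed directly by the statement that the TLFB's purpose is to calculate PHDD. Interviewers must also verify blank diary days, with no stated 7-day limit, and missed visits may be made up by telephone. This shows that staff may well collect the extra days, and that the two rules are not a word-for-word contradiction, since one is written for non-alcohol substances. But the diary is an aid to an interview whose span is fixed twice at 7 days, and telephone collection is optional. Neither extends the look-back.

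The size is also fairly challenged. Catch-up recovers less than half of the slope-precision loss (about 1.08 with complete data, 1.18 with catch-up, 1.24-1.25 without), because weeks after dropout stay lost. Table 5 comes from a partly enrolled trial of another drug. Both points stand and are why the point is minor.

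A reader might also infer that early visits cause days to be counted twice. The TLFB is a dated calendar, so asking about a day twice need not mean counting it twice; nothing in the plan shows that it would. Nor does this point justify replacing the zero-inflated negative binomial model. D.6.a already provides for checking assumptions and making modifications, and the choice of another model would be a preference.

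**Conclusion.** The point holds as a minor one. As written, the alcohol look-back leaves obtainable primary-outcome days uncollected whenever the gap exceeds 7 days, and the PHDD denominator presumes that they are known. The day counts in step 1 follow from the plan's text alone. The range of about 1 to about 39 person-weeks rests on borrowing the earlier trial's attendance and on when dropout occurs, which the documents do not show. The 5-6% on the slope SE rests on the stated simulation assumptions.

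A reader might infer that the missing days bias the NAC-placebo comparison, since heavier drinkers may miss more visits. The documents do not support that. Even with missed visits rising from 0% to 22% with heavy days, a 20-point arm difference moved by no more than 0.2 points, and its SE by less than 1% in every case. It would also be wrong to read all 46 missed weeks as lost to the 7-day rule: some follow dropout, and some may be replaced by telephone.

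**What to change.** 1. Reconcile the two look-back rules in D.4.d.1. At each visit or telephone contact, collect alcohol TLFB for all days since the last day already recorded, using the diary card. Enter each dated day once and assign it to its study week.
2. Restate the PHDD denominator as days with TLFB data, so that uncollected days are not counted as non-heavy.

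The planned model can stay. The cost is a few sentences of wording, a few more interview minutes after a gap and somewhat longer recall. On time, the protocol's own figure is reassuring: "It takes 5-10 minutes to complete the TLFB for a 28-day period". No extra visits, staff or participants are needed.

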Vital signs (temperature, heart rate, and blood pressure) will be measured weekly. Weight will be monitored monthly. The results will be recorded on a Vital Signs Form.

D.4.c.6. CONCOMITANT MEDICATIONS

All concomitant medications (prescription or over-the-counter medications) taken at the time of screening as well as those started during the study will be documented on a Concomitant Medication Form completed weekly.

D.4.c.7. CONCOMITANT TREATMENT

All concomitant treatments for mental health and well-being, with a focus on alcohol and substance use, PTSD and TBI will be recorded on a monthly basis. At screening, participants will be asked to report on the history of the mental health treatment. At weeks 4, 8, and 12 they will be asked to report on any new treatments they have started while in the study. Information will be recorded on the Concomitant Treatment form.

Veterans Alcohol TBI

D.4.c.8. ADVERSE EVENT (AE) MONITORING

All adverse events that occur between the first study-related procedure and the last study-related procedure will be reported. Serious adverse events occurring within 30 days following the last dose of study medication will also be handled according to this procedure. Those meeting the definition of serious adverse events will be reported using the Serious Adverse Event Form. Active monitoring of Adverse Events (AEs) will begin as soon as a study participant initiates study treatment, and will continue until the end of study for each participant. AEs will be monitored weekly in two ways:

- a. An open-ended question will be asked about presence of any AEs weekly (AE Spontaneous).
- b. A checklist of expected topiramate-related AEs will be asked of each participant weekly (AE Checklist).
- All Adverse Events will be recorded on the appropriate forms.

D.4.d. Alcohol and Substance Use Measures

D.4.d.1. TIMELINE FOLLOWBACK (TLFB)

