At subsequent visits, if the participant's BrAC is greater than 0.025%, study clinician will assess whether or not the participant may complete the study visit. The participant may be asked to wait until the breathalyzer test is lower, or he/she may be asked to complete the visit at another time. If the participant is unwilling or unable to remain at the site until their BrAC returns to 0.025%, study medication will be dispensed but additional study procedures will not be completed. Breath Alcohol Concentration (BrAC) –will be measured weekly. Study visits that include neurocognitive testing require complete sobriety (0.00%). If a participant's BrAC is greater than 0.00% the participant will wait until BrAC returns to normal or complete the visit on another day. Purpose: To ensure that the participant is sober enough to perform the required study activities. Time required for administration: 1 minute. Frequency of administration: This test will be administered at each weekly visit.

D.4.d.4. URINE DRUG SCREEN (UDS)

Urine Drug Screen (UDS): Urine drug testing for opioids, cocaine, cannabis (THC), and amphetamine/methamphetamine at baseline. The test will be performed by the SF VAMC Clinical Laboratory. Purpose: To provide data for descriptive purposes, and provide data for exploratory outcomes on substance use other than alcohol. Time required for administration: Collecting the urine sample should take less than 5 minutes. Analysis may take 1 to 3 days (estimate). Frequency of administration: The urine drug screens are conductet at baseline screening and weeks 4, 8, and 12.

D.4.d.5. ETHYL GLUCURONIDE (EtG)

Ethyl Glucuronide (EtG), is a non-volatile, water-soluble, stable, direct metabolite of ethanol that is currently used in clinical research for alcohol treatment to detect recent alcohol use, up to approximately 80 hours post consumption¹⁴⁰. EtG is considered a sensitive and specific marker that enables detection of small amounts of alcohol in cases where neither traditional biological state markers of alcohol intake nor clinical impression gave an indication for lapse or relapse¹⁷³. EtG also validates self-report measures such as TLFB and AUDIT. Purpose: To provide an objective biological measure that detects recent alcohol consumption and verifies self-reported alcohol use within the last 80 hours. Time required for administration: Collecting the urine

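### At weeks 1, 2, 3, 5, 6 and 7 a participant above 0.025% BrAC can leave with study drug and the rest of the visit undone; the make-up is only optional, and the 7-day alcohol TLFB does not refill the lost week

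*Combined protocol and SAP*

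**What the plan says.** D.4.d.3 (Breath Alcohol Concentration) sets out steps for a reading above 0.025% at any visit after consent. A study clinician judges whether the visit can proceed. The participant may be asked to wait, or to finish the visit on another occasion. For someone who will not or cannot wait, "study medication will be dispensed but additional study procedures will not be completed". Visits with neurocognitive testing need a reading of 0.00%, and there the participant either waits or returns another day.

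D.4.a (Overview) has general provisions for missing data. "All research assessments should be completed within an established window", which is ±3 days for weeks 1, 2, 3, 5, 6 and 7. In addition, "some self-report and interview measures may be administered by telephone to collect missing data from patients unwilling or unable to visit research sites". "All phone visits will include a Medical Management counseling session", and the investigator files a protocol violation if that session proves impossible.

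D.4.d.1 (Timeline Followback) fixes the recall period for alcohol: "the TLFB will be done weekly for the preceding 7 days at weeks 1-8, and at week 12". The same section collects cigarette and other substance use for the whole time since the previous visit. The TLFB supplies percent heavy drinking days (PHDD), which D.6.a models over weeks 1 to 8.

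**The concern.** Two of the plan's own commitments meet this rule. Adverse events and vital signs are to be monitored weekly (D.4.c.8, D.4.c.5), and alcohol use is to be watched at each weekly visit as a protection against relapse (E.1.b.6). Yet in the dispense-and-leave case drug supply continues while none of these checks is required.

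For the outcome, the lost week is triggered by recent drinking, which is what PHDD measures. A mixed model that uses all available data (D.3.i, study limitations) keeps the participant in the analysis, but it does not restore that week. It protects against bias only if the missingness can be explained by data that were observed. The withdrawal example in E.1.d, a 25% rise in weekly alcohol use, also cannot be worked out for a week with no TLFB.

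**Working it through.** The plan gives no figure on this point to reproduce. The check is a comparison of sections, followed by simple counts.

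**1. Visits exposed.** D.5.b and D.5.c place neurocognitive testing at weeks 4, 8 and 12, which have their own rule. That leaves weeks 1, 2, 3, 5, 6 and 7: 6 of the 8 treatment visits.

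**2. What is left out.** The rule names no procedures, so the list comes from D.5.b. BrAC and the clinician's judgement have already happened, CIWA-AD is set for the start of the visit (D.4.d.11), and a physician sets the weekly dose (D.3.g). What remains includes both adverse-event forms, concomitant medications, vital signs, TLFB, EtG and Medical Management.

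**3. How firm the make-up is.**
- Weeks 4, 8 and 12: definite (wait or return).
- Other weeks, D.4.d.3: optional, and stated before the leave clause rather than in it.
- D.4.a window: an expectation. A visit already at +3 days has 3 − 3 = 0 days left.
- D.4.a telephone: optional, for some measures, and worded for people who do not come to the site. It cannot supply vital signs.

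**4. Interval between adverse-event queries if nothing is made up.** Nominal: 7 + 7 = 14 days, against 7. For the outer limits, weeks 1, 2, 3, 5, 6 and 7 carry ±3 days, and "Assessments scheduled for weeks 4, 8, and 12, have a window of ± 1 week for completion".

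| Visit skipped | Longest interval | Same windows, no skip |
|---|---|---|
| Week 1 (from first dose) | 14 + 3 = 17 | 7 + 3 = 10 |
| Week 2 or 6 | 14 + 3 + 3 = 20 | 7 + 3 + 3 = 13 |
| Week 3, 5 or 7 | 14 + 3 + 7 = 24 | 7 + 3 + 7 = 17 |

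The skip adds 7 days in every row. The suicidality item on the adverse-event checklist asks about the time since the last study visit (D.4.a). That answer is therefore delayed rather than lost, provided the curtailed visit is not counted as the last one.

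**5. Outcome data lost if nothing is made up.** Per participant: 1/8 = 12.5% of weekly points, equivalently 7/(8 × 7) = 7/56 days. Per trial: 1/(30 × 8) = 1/240 = 0.42% per occurrence.

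**6. Length of a reach-back TLFB.** After one skipped visit it covers 14 days nominally and 24 at most. Both are inside the 28-day period that D.4.d.1 says takes 5–10 minutes, against 5 minutes for a weekly one.

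**The case against.** The strongest reply is that the protocol already deals with this. The sentence before the leave clause offers completion at another time for the same trigger, and D.4.a applies to all assessments without having to be cross-referenced. A reader might infer from the leave clause alone that no make-up exists. The documents do not support that: one exists, and the gap is only that it is optional and not linked to the person who leaves with drug.

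A reader might also infer that drug is handed over without clinical review. That is not so either. A clinician assesses the participant, a physician sets the dose and writes the prescription (D.3.g), and anyone who drove and reads above 0.08 is assessed before leaving (D.3.d). What stands is that no adverse-event query or vital signs are required first.

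The 24-day interval should not be read as 24 days of unmonitored dosing. Each visit dispenses 10 days of drug (D.3.g), so two dispensings cover at most 20 days at the scheduled dose. The case also needs adjacent visits at opposite window limits. E.1.a.2 describes oral NAC as having few clinically significant adverse effects at doses up to 8000 mg/day, against a maximum here of 3600.

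Finally, deferring self-report from someone who is not sober is a reasonable validity choice, and a wholly missed visit would lose the same weekly point. Both are fair. They weaken the case for questioning before dispensing, but not the case for longer recall at the next visit.

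**Conclusion.** The point holds as a minor one. In the dispense-and-leave case at six of the eight treatment visits, recovery of safety and outcome data is discretionary. If it does not happen, the adverse-event query is delayed by one visit (nominally 14 days between queries), and one of the participant's 8 weekly PHDD points (12.5%; 0.42% of the trial's planned points) is lost for a reason linked to drinking.

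This rests on reading the omitted procedures from the D.5.b visit list and on no make-up taking place. The documents give no rate for the event, and none is assumed here. A reader might infer that the loss favours one arm. Nothing in the documents supports a direction, since that would depend on how often each arm triggers the rule and on how much was drunk in the missing weeks.

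**What to change.** This is a cheap improvement to wording, in three parts:

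- **TLFB recall (D.4.d.1).** Let each weekly alcohol TLFB reach back to the last recorded day, as the section already does for other substances, with the existing diary card as prompt. The record is daily, so recovered days can be assigned to their own treatment week. This part works even when no visit window is left.
- **Make-up (D.4.d.3).** State that, when a participant leaves with drug, the remaining procedures will be rescheduled or done by telephone within the D.4.a window where possible.
- **Before dispensing.** Attempt vital signs and a brief adverse-event and suicidality check, pass the results to the physician setting the dose, and repeat the query at the make-up contact. Dispensing otherwise stays as planned.

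No new instrument or staff is needed. The cost is a few minutes at the visit and one make-up contact per occurrence. If that contact is by telephone it must include Medical Management, a 15–30 minute session (D.3.h) already due that week. The D.4.a protocol-violation rule for an impossible session is a reason to keep the words 'where possible'. The drawbacks are a longer recall period, and pre-dispensing answers that may be less reliable above 0.025% or may be declined.

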- Beck Anxiety Inventory (BAI): a measure of anxiety severity¹⁴⁸; well suited for monitoring change with treatment¹⁴⁸

Neurocognitive Assessment

The battery was developed to assess performance in cognitive domains commonly affected by TBI and/or alcohol use and contains standardized instruments with good-to-excellent norms administered (~1.5 hours) at baseline, Wks 4,8 and 12. Domains and constituent measures:

- Risk Taking, Decision-making, and Motor/Choice Impulsivity: Balloon Analogue Risk Task ¹⁴⁹⁻¹⁵¹; Iowa Gambling Task ¹⁵²; Stop-signal¹⁵³, Delayed Discounting¹⁵⁴⁻¹⁵⁸
- Executive Functioning: Stroop Color-Word^{159,160}, Trail Making B¹⁶¹
- Verbal Fluency: Controlled Oral Word Association Test¹⁶²
- Processing Speed: Trail Making A¹⁶¹, Stroop Color-Word^{159,160}
- Working Memory: WAIS-IV Arithmetic and Digit Span¹⁶³
- Learning and Memory:
 - Auditory-verbal: Hopkins Verbal Learning Test (HVLT-R)¹⁶⁴
 - Visuospatial: Brief Visual Memory Test-Revised^{165,166}

- Premorbid verbal intelligence: Wechsler Test of Adult Reading^{167,168}
- Alcohol Approach Bias: Alcohol Approach Task (AAT)²⁰⁹

Raw scores are converted to z-scores based on norms. Domain-specific summary score will be calculated by averaging z-scores of the constituent measures. To minimize practice effects, when feasible, alternate forms will be used for repeated administrations.

Statistical Plan and Data Analysis

The proposed study has primary and exploratory outcomes.

Primary Outcome

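### At weeks 4, 8 and 12 the zero-breath-alcohol rule covers the whole visit, so rebooking makes EtG timing depend on drinking and leaves gaps and overlaps in the 7-day drinking record

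*Combined protocol and SAP*

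**What the plan says.** Two breath rules stand in D.4.d.3.

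- At visits after consent, "if the participant's BrAC is greater than 0.025%, study clinician will assess whether or not the participant may complete the study visit". For a participant who cannot or will not stay, "study medication will be dispensed but additional study procedures will not be completed".
- Visits with neurocognitive testing require 0.00%. Above that, "If a participant's BrAC is greater than 0.00% the participant will wait until BrAC returns to normal or complete the visit on another day".

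D.3.i places the cognitive battery, described as "standardized instruments with good-to-excellent norms administered (~1.5 hours) at baseline, Wks 4,8 and 12", at baseline and three later visits. The visit lists in D.5.b and D.5.c put EtG and the TLFB in the week 4, 8 and 12 visits.

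On timing, D.4.a states: "Assessments scheduled for weeks 4, 8, and 12, have a window of ± 1 week for completion". D.4.d.5 describes EtG as a test "to detect recent alcohol use, up to approximately 80 hours post consumption", whose purpose is to verify self-reported drinking. D.4.d.1 sets alcohol recall "for the 7-day period prior to each weekly visit". The same section has cigarettes and other substances recorded from one visit to the next, but does not say this for alcohol.

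The EtG schedule is itself inconsistent. D.3.i lists EtG among measures taken at baseline and weeks 4, 8 and 12, whereas D.4.d.5 and D.5.b have it weekly.

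**The concern.** Sobriety matters for valid cognitive testing. A urine sample does not need a zero reading, and the TLFB is a short retrospective interview supported by a diary card. Because the 0.00% rule is written for the visit, both can move with the battery.

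A reading above zero means that alcohol is present, so urine taken then would be expected to be EtG-positive. If the visit is rebooked, the sample is taken on a later day that must also read 0.00%. The timing of the objective measure then depends on the behaviour it measures. At stake are EtG's value as a check on self-report and the continuity of the daily record behind percent heavy drinking days (PHDD). Neither a missed sample nor an unrecorded day can be reliably recovered at analysis.

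**Working it through.** The documents give no figure for this point, so there is none to reproduce.

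**1. EtG.** The window after the nominal date is 7 × 24 = 168 hours. The detection limit is about 80 hours, or 80/24 = 3.3 days. A same-day wait costs only hours. A delay of one or two days (24–48 hours) stays inside the limit. From four days (96 hours) the drinking behind the reading is out of range. The positive is lost only if the participant has also not drunk in the 80 hours before the new sample.

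How likely is such a dry spell? As a rough guide, assume independent days and at least three consecutive dry ones. The TBI group in Table 2 (C.5) drank on 5.3 days a week at baseline: ((7 − 5.3)/7)³ = (1.7/7)³ ≈ 1.4%. If treatment halved drinking days to 50% (assumed): 0.5³ = 12.5%.

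**2. TLFB.** Put the week *w* visit on day 7*w*, recalling days 7(*w* − 1) to 7*w* − 1. Let week 4 slip by *k* = 5 days, with other visits on schedule.

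- Week 3 (day 21) covers days 14–20.
- Week 4 (day 33, not 28) covers days 26–32.
- Week 5 (day 35) covers days 28–34.

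Days 21–25 are never recorded, and days 28–32 are recorded twice. In general *k* days are lost and *k* duplicated. Moving week 8 from day 56 to day 61 loses days 49–53 and counts days 56–60 as week 8. The recall still contains day 27, the eve of the failed attempt, for any *k* up to 6.

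**3. Size.** The rate of positive readings, the delay and the share who wait are not given, so a simulation used assumed values:

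- 30,000 participants per arm, mean PHDD 60% and 40%
- day-to-day persistence of 0 or 0.4
- a 10%, 25% or 50% chance of a positive reading after a heavy day
- a delay of 1 day, uniform 1–7 days, or 7 days
- 0% or 50% waiting the same day
- as a proxy for EtG, any heavy day in the last three

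Rows below have persistence 0.4. Figures are percentages, scheduled → recorded, heavier arm / lighter arm.

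| Scenario | Week 4/8 PHDD | EtG proxy | Weeks 1–8 difference |
|---|---|---|---|
| 25% positive, none wait, 1 day | 60.2→60.5 / 39.9→40.2 | 78.1→78.1 / 58.8→58.8 | 20.3→20.3 |
| 25%, half wait, 1–7 days | 60.0→59.9 / 40.0→40.0 | 77.9→77.1 / 58.7→57.9 | 20.0→20.0 |
| 25%, none wait, 7 days | 59.9→58.6 / 40.1→38.9 | 77.8→75.2 / 58.5→55.4 | 20.1→20.1 |
| 50%, none wait, 7 days | 60.1→55.8 / 40.2→36.7 | 78.1→70.9 / 58.6→51.0 | 19.9→19.9 |

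In the last row recorded PHDD falls by 4.3 and 3.5 points and the EtG proxy by 7.2 and 7.6 points. About 11% and 5% of week 4/8 records count as missed. The week 4/8 arm difference shrinks by 0.8 point (19.9→19.1), the largest shrinkage found. Across all scenarios the weeks 1–8 difference changed by about 0.1 point at most. One reason is that only 2 of the 8 weeks in the primary model (D.6.a) fall under the 0.00% gate. Week 12 is not in that model.

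**The case against.** The rule lets the participant wait, and a same-day wait removes the problem. Completing a visit on another day could mean finishing what was begun, and no passage forbids taking urine from someone who is present. Only the 0.025% rule expressly leaves procedures undone. D.4.a asks staff to schedule as close as possible to the protocol date, so a full week's slip should be unusual. EtG is exploratory. If it is collected weekly, most treatment-phase samples escape the 0.00% gate. With 15 per arm and assumed positive rates of 70% and 50%, the standard error of the difference is √(0.7 × 0.3/15 + 0.5 × 0.5/15) ≈ 17.5 points per visit, far above any plausible distortion.

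Most of this stands, and it limits the size of the point. It does not remove it. The text is at best silent on what is collected at a failed attempt, and site staff following it literally would move everything. If the D.3.i schedule governs, every post-baseline EtG sample is gated at 0.00%. The telephone provision in D.4.a could recover some TLFB data, but not urine.

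A reader might infer more: that drinking is under-counted specifically in the heavier-drinking arm, that records drift towards drier days, and that the treatment difference is diluted accordingly. The documents do not support this. The simulated EtG loss was about as large in the lighter arm. A delay under 7 days keeps the drinking behind the reading, and a 1-day delay moved recorded PHDD by 0 to +0.8 point.

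**Conclusion.** The point holds as a modest design defect. When a week 4, 8 or 12 visit is rebooked because of the breath reading, EtG timing depends on drinking and a positive can be lost. For alcohol TLFB, each day of delay at week 4 loses one day and duplicates another, with other visits on schedule. That arithmetic needs no assumption about the arms.

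The likely harm is to EtG as a check on self-report and to the completeness of the daily record. Under the most adverse assumptions tried, the EtG proxy fell by about 7 points in both arms. The effect on the primary PHDD comparison is likely small, and a difference between arms is not shown. All sizes rest on assumed rates of positive readings, delay and waiting. If everyone waits the same day, the TLFB is unaffected and EtG loses only hours of its window.

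**What to change.** - In D.4.d.3, limit the 0.00% requirement to the neurocognitive battery and rebook only that.
- Collect urine for EtG at the first attended attempt whatever the breath reading. State this as an exception to both breath rules.
- Complete the TLFB once the participant can be interviewed, the same day or by telephone under D.4.a. In D.4.d.1, tie alcohol recall to calendar dates since the last recorded day.
- Do not simply place the TLFB and NSI under the 0.025% rule, because it leaves procedures undone for a participant who will not wait. Give the NSI its own line, since a symptom scale completed with alcohol on board has a validity cost of its own.
- Log breath readings, failed attempts and delays, and tabulate them by arm.
- Reconcile the EtG schedule in D.3.i with D.4.d.5 and D.5.b.

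The cost is a wording change and a short log. D.4.d.5 puts urine handling at under 15 minutes and D.4.d.1 puts a weekly TLFB at 5. The downside is that the battery and the other measures may fall on different days for some participants.
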